**Footnotes:**

(X) optional assessments at discretion of investigator

 For each patient, the main trial and study partner consents must be obtained. Optional consents include biobanking and speech analysis.

 The screening period may take up to 35 days with 2 visits. At the second screening visit, urine drug screen may be repeated at discretion of investigators (X) if needed.

 Safety lab and/ or drug screen test (urine), may be performed more frequently based on investigator discretion or if required locally.

 Pregnancy tests are required for women of child-bearing potential only and may be performed more frequently based on investigator discretion or if required locally. If urine (dipstick) pregnancy test is positive, a serum test is required.

 PK pre-dose/ trough sample collection within 30 minutes before IMP dosing. Note: No IMP dosing is applicable to EOT or eEOT visit. PK sample should be taken approximately 24 hours post last dose at the EOT. PK sample should be taken as applicable at the eEOT. For further details please refer to [Section 5.3](#) and [Appendix 10.1](#).

 One sample for DNA biobanking will be taken, preferably at Visit 2. However, collection at a later visit is permitted as long as the informed consent for biobanking remains valid. Sample for Plasma and Serum banking purposes will be taken at V2 before first IMP intake and again at (e)EOT.

 Duration of assessments and visits indicated in this [Flow Chart](#) are approximate estimates, actual time may vary as per site and patient requirements.

 At visit 2, the MINI does not need to be repeated however the results from visit 1 should be confirmed and documented in the source documents.

 All Baseline assessments must be completed prior to IMP intake at visit 2.

 Haematology panel A and B only.

Proprietary confidential information © 2024 Boehringer Ingelheim International GmbH or one or more of its affiliated companies

 Patients who finish the 26 weeks of treatment period in this study, can rollover to the extension trial either after completing the EOT visit (preferred option) or within 2 weeks of EOT (i.e. at scheduled FU1 including vitis window).

 Visit 11 will be performed only by patients who discontinue early from trial drug but agree to attend further visits according to protocol.

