### **3.3.4.2      Permanent Discontinuation of Trial Treatment**

For all patients the reason for permanent discontinuation from trial treatment (e.g. adverse events) must be recorded in the eCRF. Patients who permanently discontinue from the trial after randomization will not be replaced.

Even if the trial treatment is permanently discontinued, the patient should remain in the trial and, given the patient’s agreement:

- The patient will complete the early end of treatment and safety follow up visits.
- Additionally, the patient will be followed according to the [Flow Chart](#) until the planned Visit 11 (26 weeks).

Please refer to [Flow Chart](#) and [Section 6.2.5](#) for more information on continued trial participation.

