### 5.2.6.2 Adverse event collection and reporting

#### 5.2.6.2.1 AE Collection

The investigator shall maintain and keep detailed records of all AEs in the patient files.

The following must be collected and documented on the appropriate CRF(s) by the investigator:

- **For patients who roll-over to the extension trial:**
  - From signing informed consent onwards until first dose of trial medication in the extension trial: all AEs (serious and non-serious) and all AESIs. Updates to

concomitant therapy should also be included until first dose of trial medication in the extension trial.

**Note:** Updates for SAEs and/ or AESIs ongoing at the time of rollover to the extension trial, must be also updated in parent trial, in addition to the extension trial, as long as the data base of parent trial is not locked. On SAE form, updates for events reportable on SAE form with onset in parent trial are only reported into the parent trial.

- **For patients who do not roll-over to the extension trial:**
  - From signing the informed consent onwards until the 28 days (F2 visit) after the end of treatment visit: all AEs (serious and non-serious) and all AESIs.
  - **After the individual patient's end of trial:** The investigator does not need to actively monitor the patient for new AEs but should only report any occurrence of cancer and trial treatment related SAEs and trial treatment related AESIs of which the investigator may become aware of by any means of communication, e.g. phone call. Those AEs should be reported on the BI SAE form (see section 5.2.6.2.2), but not on the CRF.
- **For patients who permanently discontinue trial medication prematurely:**
  - From signing the informed consent onwards until the 28 days (Follow-up 2 visit) after the early end of treatment visit: all AEs (serious and non-serious) and all AESIs.
  - **From Follow-up 2 visit up to the individual patients' planned end of Trial (i.e. 26 weeks/visit 11):** Until the individual patient's planned end of trial, the investigator must report
    - Treatment related SAEs / AESIs
    - Following regardless of causal relationship
      - Anaemia
      - SAEs from C-SSRS assessments
      - Any occurrence of cancer
      - Deaths/ fatal AEs

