6. GENERAL ANALYSIS DEFINITIONS

6.1 TREATMENT(S)

For basic study information on treatments to be administered, assignment of treatment groups, select of doses, see CTP Section 4.

Table 6.1: 1 lists the two treatment groups in this study. Table 6.1: 2 defines the analysing treatment period for safety analyses. For this study, the residual effect period (REP) is defined as 12 days after the last dose of trial medication.

Table 6.1: 1 Treatment descriptions

Long Name	Short Name
Placebo	Placebo
Iclepertin 10 mg QD	Iclepertin 10 mg

Table 6.1: 2 Analysing treatment periods (same for all treatment groups)

Analysing Treatment Period	Start Date	End Date
Screening period	Date of informed consent	Date of the first treatment administration – 1 day
On-treatment period	Date of the first treatment administration	Date of the last treatment administration + REP
Post-treatment period	Date of the last treatment administration + REP + 1 day	Date of the last per protocol visit

REP is the residual effect period which is defined as 12 days after the last dose of trial treatment.

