7.8.1 Adverse events

Unless otherwise specified, the analyses of AEs will be descriptive in nature. All analyses of AEs will be based on the number of subjects with AEs and not on the number of AEs. The reporting and analyses of AEs will follow the BI guideline (3). AEs will be coded with the most current version of MedDRA®.

For further details on summarization of AE data, please refer to (1, 3).

The analysis of AEs will be based on the concept of treatment emergent AEs. That means that all AEs occurring between the date of the first administration of trial treatment till the date of the last administration of trial treatment + residual effect period will be assigned to the on-treatment period. All AEs occurring before the first administration of trial treatment will be assigned to 'screening' and all AEs occurring after the residual effect period will be assigned to 'follow-up'. For details on the treatment definition, see [Section 6.1](#).

Adverse events of special interest (AESIs)

A hepatic injury is defined by the following alterations of hepatic laboratory parameters:

- an elevation of AST and / or ALT ≥ 3 fold ULN combined with an elevation of total bilirubin ≥ 2 fold ULN measured in the same blood draw sample; and / or
- marked peak aminotransferase (ALT and / or AST) elevations ≥ 10 fold ULN.

See CTP Section 5.2.6.1.

Other significant AEs

User-defined AE category	MedDRA preferred terms	
Drug abuse, dependence, withdrawal and substance-related disorders, including diversion	Accidental death	Intentional overdose
	Drug abuse	Muscle rigidity
	Accidental overdose	Nasal necrosis
	Accidental poisoning	Nasal septum perforation
	Dependence	Nasal septum ulceration
	Drug abuser	Needle track marks
	Product administered at inappropriate site	Neonatal complications of substance abuse
	Drug dependence	Overdose
	Drug detoxification	Poisoning
	Drug dependence antepartum	Poisoning deliberate
	Drug dependence, postpartum	Substance dependence
	Drug diversion	Prescription form tampering
	Drug tolerance	Product tampering
	Drug tolerance increased	Product used for unknown indication
	Toxicity to various agents	Rebound effect
	Drug use disorder	Seizure
	Drug use disorder antepartum	Status epilepticus
	Drug use disorder, postpartum	Substance abuse
	Drug withdrawal convulsions	Substance abuser
	Drug withdrawal headache	Substance use
	Drug withdrawal syndrome	Substance use disorder
	Drug withdrawal syndrome neonatal	Substance-induced mood disorder

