An overall summary of adverse events will be presented, including frequency of schizophrenia relapse. The frequency of subjects with AEs will be summarised by treatment, primary system organ class (SOC) and preferred term (PT). The SOCs will be sorted by default in descending frequency and PTs will be sorted in descending frequency within an SOC in the iclepirtin arm. Separate tables will be provided for patients with

- Related AEs
- Serious AEs
- Serious related AEs
- AESIs
- Other significant AEs
- AEs leading to death
- AE leading to discontinuation of trial medication
- AEs occurred with incidence in the preferred term >2%
- AEs suggestive of abuse potential or related to CNS depressant effects
- AEs in user-defined AE categories
- AEs occurred during the follow-up period.

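### The follow-up AE table pools full and restricted event collection in patients who stop treatment early; it should be split at Follow-up 2

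*SAP*

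**What the plan says.** **SAP.** Section 7.8.1 counts AEs as treatment-emergent up to the last dose plus the residual effect period, which Section 6.1 says is "defined as 12 days after the last dose of trial medication". After that, "all AEs occurring after the residual effect period will be assigned to" a follow-up category. Section 7.8.1 gives this category no end date but refers to Section 6.1. There, Table 6.1: 2 ends the post-treatment period at "Date of the last per protocol visit". The list of separate tables in 7.8.1 includes one for "AEs occurred during the follow-up period". AE analyses count subjects with events, and the visible text states no adjustment for observation time.

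**Protocol, visits.** Patients who stop treatment early are asked to stay in the trial to Week 26 (Section 3.3.4.2). Flow Chart footnote 12 says: "Visit 11 will be performed only by patients who discontinue early from trial drug but agree to attend further visits according to protocol".

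**Protocol, AE collection (Section 5.2.6.2.1).** For early stoppers the full rule runs "From signing the informed consent onwards until the 28 days (Follow-up 2 visit) after the early end of treatment visit: all AEs". From Follow-up 2 to Visit 11 the investigator must report only treatment-related SAEs and AESIs and, whatever the cause, anaemia, SAEs from the C-SSRS, cancer and deaths. Completers who do not roll over are under the full rule to Follow-up 2, which is the end of their trial.

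**The concern.** The SAP's follow-up category is longer than the protocol's safety follow-up, and the collection rule changes inside it. Before Follow-up 2 any AE is recorded. Afterwards a headache or a bout of insomnia need not be, while anaemia must be. A table that counts subjects with each preferred term over the whole period treats these events as having had the same chance of being recorded.

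This table is the visible SAP's dedicated display of off-drug AEs. Protocol Table 1.4.2:1 notes that AEs after stopping the drug have not been formally investigated, and Section 5.2.6.6 asks for close monitoring after stopping in patients who do not roll over. A reader will therefore use the table to judge which kinds of event occur off drug. That mix would partly reflect what sites were told to collect.

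**Working it through.** The documents state no follow-up AE frequency, so there is no planned figure to reproduce. The check is day arithmetic.

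**Inputs**
- Residual effect period: 12 days (SAP 6.1).
- eEoT visit: 0 to 7 days after the last dose (Protocol 6.2.5.1).
- Follow-up 2: 28 days after eEoT, window +7 days (Flow Chart; Protocol 6.2.5.2).
- Visit 11: day 183 (Flow Chart).
- Assumptions: the stop day, attendance to Visit 11, no restart of treatment, and sites recording only the required minimum.

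**Formulas.** Let *s* be the day of the last dose and *d* the days from last dose to Follow-up 2. Then *d* runs from 0 + 28 + 0 = 28 to 7 + 28 + 7 = 42, with 35 as the middle value.
- Full-collection days in the follow-up category = *d* − 12.
- Restricted days = max(0, 183 − (*s* + *d*)).

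**Single patients, *d* = 35** (full days = 35 − 12 = 23)

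| Last dose, day | Full days | Restricted days | Restricted share |
|---|---|---|---|
| 43 | 23 | 183 − 78 = 105 | 105/128 = 82% |
| 85 | 23 | 183 − 120 = 63 | 63/86 = 73% |
| 127 | 23 | 183 − 162 = 21 | 21/44 = 48% |
| 148 or later | 23 | 0 | 0% |

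**Average over stop days, uniform on days 1 to 182 (assumed)**

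| *d* | Full days | Mean restricted days | Restricted share | Patients with any restricted time |
|---|---|---|---|---|
| 28 | 16 | (154 × 155/2)/182 = 65.6 | 65.6/81.6 = 80% | 154/182 = 85% |
| 35 | 23 | (147 × 148/2)/182 = 59.8 | 59.8/82.8 = 72% | 147/182 = 81% |
| 42 | 30 | (140 × 141/2)/182 = 54.2 | 54.2/84.2 = 64% | 140/182 = 77% |

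**Completers who do not roll over.** Their last dose is the day before EoT (Protocol 4.1.4), so Follow-up 2 falls 29 to 36 days after it. They have 29 − 12 = 17 to 36 − 12 = 24 full-collection days and no restricted days.

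**What this does to a frequency (illustration).** Take a last dose on day 85, *d* = 35, and two event types with the same assumed true rate of 0.005 per day.
- Collected throughout, as anaemia is: 1 − exp(−0.005 × 86) = 35% of subjects.
- Collected only to Follow-up 2, as a non-listed, non-serious event is: 1 − exp(−0.005 × 23) = 11%.

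The threefold gap comes from the collection rule alone. The rate is chosen for illustration and is not a forecast.

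**How many patients.** Protocol 7.5 projects 30% to 40% early termination: 0.30 × 293 = 88 to 0.40 × 293 = 117 per arm. How many of these would be followed for AEs to Visit 11 is not stated.

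**The case against.** **Only one descriptive table is affected.** No hypothesis testing is planned for safety, and the main AE tables stop at last dose plus 12 days. This stands, and it makes the point minor.

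**The restricted list is a minimum.** Section 5.2.6.2.1 says what must be reported. The Flow Chart marks adverse events at every visit through Week 26, and its footnotes do not state the restriction, so some sites may record more. This stands as a limit on the 64% to 80% figure. It does not restore a single rule: collection would then vary by site as well as by time.

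**An internal AE guideline may define a cut.** SAP 7.8.1 defers to a sponsor guideline that is not in the documents. That is possible, but the SAP's own Table 6.1: 2 points to the last visit, and no split is visible.

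**A cut at Follow-up 2 does not equalise everyone.** Patients who roll over stop contributing at the first extension dose. At the latest planned time, 14 days after EoT, that is 15 days after the last dose, 3 days past the residual effect period (6 with the visit window). This stands, but it concerns how long patients are observed. It does not justify pooling two collection rules.

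**A stronger reading to avoid.** A reader might infer that the table will exaggerate off-drug anaemia on iclepertin, because haemoglobin falls trigger withdrawal and phase II showed a larger mean fall on 10 mg than on placebo. The documents do not support this. Under Alert 3 (Protocol 5.2.6.4) anaemia is reported when the withdrawal criterion is met, so its onset normally falls in the on-treatment period. Only a new onset more than 12 days after the last dose would enter the follow-up table. Protocol 4.1.5.1 also reports that the number of patients with a haemoglobin fall above 2 g/dL was the same on placebo as in the active arms. Likewise, assigning the two ends of the 30% to 40% range to the two arms would give 0.40/0.30 = 1.33 times the restricted time in one of them. That range is planning uncertainty for the whole trial, and no section projects different stopping by arm.

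**Conclusion.** The mismatch is real on the text. One follow-up table would pool AEs from last dose plus 12 days to the last per protocol visit, while the collection rule for early stoppers narrows at Follow-up 2. That the table runs to Visit 11 follows from reading SAP 7.8.1 with Table 6.1: 2 and the protocol; 7.8.1 does not say so itself.

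The consequence is that mandated events such as anaemia can look more frequent relative to ordinary AEs. With uniform stop days, follow-up to Visit 11 and minimum recording, 64% to 80% of these patients' time in the category is under the restricted rule. Patients whose last dose falls after about day 140 to 154, depending on visit timing, have no restricted phase.

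The size and direction of any difference between arms cannot be derived from the documents, since they depend on stopping rates, timing and retention by arm. The treatment-emergent tables are unaffected. This is a cheap improvement to one descriptive output and does not threaten the trial's safety conclusions.

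**What to change.** In SAP 6.1 and 7.8.1, end the period used for the follow-up AE table at Follow-up 2, with its visit window, for all patients. Show events with onset after Follow-up 2 up to Visit 11 in a separate labelled table or listing. It should state the restricted collection rule of Protocol 5.2.6.2.1 and give, per arm, the number of early stoppers followed beyond Follow-up 2.

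The cost is one date cut-off in the AE period derivation and one small extra output. No new data are needed. A footnote on the pooled table would warn the reader but would leave the mixed frequencies in place.

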### **1.2.5 Data from clinical studies**

To date, Iclepertin has been well tolerated and has demonstrated a good safety profile. A total of 323 healthy subjects have received  $\geq 1$  dose of Iclepertin. In addition, 339 patients with schizophrenia and 490 patients with Alzheimer's disease have been treated with Iclepertin for 12 weeks. The most frequent AEs were related to the Central Nervous System (CNS), with headaches the most common and more frequent in the active groups than in placebo groups. Dizziness, somnolence and gastrointestinal disorders, such as nausea and vomiting, were also among the AEs reported more frequently on Iclepertin than placebo.

Phase II trials of 12-week treatment duration in patients with schizophrenia and Alzheimer's disease, like trials with other GLYT1 inhibitors such as bitopertin [[R15-1266](#), [R18-1054](#)], detected an impact of Iclepertin on haemoglobin (Hb) levels. There was a slight decrease in Hb across the active treatment groups, compared to placebo. It should be however noted that majority of patients (over 90%) remained in the range of normal values.

There were no other clinically relevant findings in the clinical laboratory evaluation, 12-lead electrocardiogram (ECG), assessment of vital signs, or visual tests. No signal was observed for suicidal ideation or behaviour.

In the Phase II trial, 1346-0009, in patients with schizophrenia, proof of clinical concept (PoCC) was demonstrated. Iclepertin improved cognition assessed as the change from baseline in MCCB (Measurement and Treatment Research to Improve Cognition in Schizophrenia [MATRICS] consensus cognitive battery) overall composite T-score after 12-week treatment (the primary endpoint). The largest improvements from baseline versus placebo were observed in the 10 and 25 mg dose groups; the 25 mg dose did not appear to provide an additional benefit over the 10 mg dose. Moreover, the 10 mg group showed most consistent efficacy across various analyses.

In the Phase II trial, 1346.23, in patients with mild to moderate AD, results showed no evidence for efficacy of Iclepertin compared with placebo for the evaluated endpoints.

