### **1.4.2 Risks**

The overall safety profile of Icleperin is outlined in the current IB ([c02155957](#)).

In the Phase II trial 1346-0009, no dose dependency was observed for the overall number of AEs. The frequency of patients with SAEs was low and was comparable across all treatment groups. The frequency of patients with AEs leading to discontinuation of trial medication was also low. There were no deaths.

Table 1.4.2:1 Overview over trial related risks

| Possible/ known risks of clinical relevance for this trial   | Summary of data, rationale for the risk  | Mitigation strategy  |
|--|--|--|
| Investigational Medicinal Product   |  |  |
| 
The most frequent AEs were CNS-related
 

• Headache-reversible and can be clinically monitored.

• Somnolence (drowsiness)

 | 
These effects are understood to be typically mild to moderate and transient.
 
Refer to IB for more details.
   | 
Management of symptoms, evaluation, and follow-up as needed to ensure subject safety, per investigators clinical judgment.
  |
| Decrease in Hb   | 

• GLYT1 is present on erythrocyte precursors in the bone marrow and on circulating reticulocytes and glycine is required for Hb synthesis.

• No clear decrease in Hb was seen in Iclepertin -treated subjects compared to placebo in phase I.

• In Phase II, the mean decrease in Hb was observed for 10 mg and 25 mg compared to placebo [10 mg: -3.3 g/L (-0.33 g/dL); 25 mg: -4.5 g/L (-0.45 g/dL); placebo: -0.5 g/L (0.05g/dL)]

 | 

• Patients with haemoglobin (Hb) below lower limit of normal at Visit 1 assessed by the central lab will be excluded from participation in this study.

• For other GLYT1 inhibitors maximum decrease in Hb was observed after 4 months of treatment, Hb will be checked at Visit 9.

• Please refer to section 5.2.6.4 'Haemoglobin and anemia' for more details.

 |

Table 1.4.2:1 Overview over trial related risks (con't)

| Possible/ known risks of clinical relevance for this trial | • Summary of data, rationale for the risk  | • Mitigation strategy  |
|--|--|--|

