	Generalised tonic-clonic seizure	Substance-induced psychotic disorder
	Hangover	Treatment noncompliance
	Intentional product misuse	Withdrawal syndrome
Euphoria-related adverse events	Dizziness	Feeling drunk
	Euphoric mood	Feeling of relaxation
	Feeling abnormal	Inappropriate affect
CNS depressant effects	Depressed level of consciousness	Sedation
	Fatigue	Sluggishness
	Hypersomnia	Somnolence
	Lethargy	Stupor
	Loss of consciousness	
Stimulation and anxiety-related adverse events	Agitation	Morbid thoughts
	Anxiety	Nervousness
	Anxiety disorder	Panic attack
	Anticipatory anxiety	Panic disorder
	Energy increased	Panic reaction
	Fear	Psychogenic tremor

	Fear of death	Psychomotor hyperactivity
	Feeling jittery	Restlessness
	Generalised anxiety disorder	Tension
	Hypervigilance	
Perceptual disturbances / psychotomimetic effects	Abnormal dreams	Hypoesthesia
	Acute psychosis	Ideas of reference
	Aggression	Illogical thinking
	Alice in wonderland syndrome	Illusion
	Altered state of consciousness	Incoherent
	Altered visual depth perception	Indifference
	Anger	Jamais vu
	Communication disorder	Loose associations
	Confusional state	Magical thinking
	Consciousness fluctuating	Nightmare
	Déjà vu	Paranoia
	Delirium	Paroxysmal perceptual alteration
	Delusion	Psychotic behaviour
	Delusion of grandeur	Psychotic disorder
	Delusion of reference	Psychotic symptom
	Delusion of replacement	Reactive psychosis
	Delusional perception	Rebound psychosis
	Derailment	Sensory disturbance
	Disinhibition	Sensory level abnormal
	Disorientation	Slow speech
	Dysarthria	Somatic delusion
	Flight of ideas	Somatic hallucination
	Formication	Staring
	Hallucination	Suspiciousness
	Hallucination, auditory	Tangentiality
	Hallucination, gustatory	Thinking abnormal
	Hallucination, olfactory	Thought blocking
	Hallucination, synaesthetic	Thought broadcasting
	Hallucination, tactile	Thought insertion
	Hallucination, visual	Thought withdrawal
	Hallucinations, mixed	Transient psychosis
	Hostility	
Dissociation	Daydreaming	Hypogeusia
	Depersonalisation/derealisation disorder	Metamorphopsia
	Derealisation	Ocular discomfort
	Diplopia	Oral dysaesthesia
	Dissociation	Oral hyperesthesia

	Dissociative disorder	Pain threshold decreased
	Dissociative identity disorder	Paraesthesia
	Dysaesthesia	Paraesthesia oral
	Dysaesthesia pharynx	Pharyngeal hypoesthesia
	Dysgeusia	Pharyngeal paraesthesia
	Dysmetropsia	Photophobia
	Feeling cold	Photopsia
	Feeling hot	Synaesthesia

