The grouping of “ocular events” includes all MedDRA preferred terms under the SOC of “eye disorder” regardless of primary or secondary SOC.

Anaemia

Anaemia will be analyzed by BI customized medical query (BIcMQ) of Decreased haemoglobin and anaemia (incl. non-haematological causes), as defined in [Table 7.8.1: 2](#)

In addition, Standardised MedDRA Query (SMQ) of Haematopoietic cytopenias will be analyzed.

Table 7.8.1: 2 MedDRA preferred terms for BIcMQ of Decreased haemoglobin and anaemia (incl. non-haematological causes)

User-defined AE category	MedDRA preferred terms	
Decreased haemoglobin and anaemia (incl. non-haematological causes)	Anaemia	Haemoglobin abnormal
	Anaemia Heinz body	Haemoglobin decreased
	Anaemia folate deficiency	Haemolytic anaemia
	Anaemia macrocytic	Haemolytic anaemia enzyme specific
	Anaemia megaloblastic	Haemolytic icterohaemorrhagic anaemia
	Anaemia of chronic disease	Hyperchromic anaemia
	Anaemia of malignant disease	Hypochromic anaemia

Anaemia postoperative	Hypoplastic anaemia
Anaemia splenic	Iron deficiency anaemia
Anaemia vitamin B12 deficiency	Leukoerythroblastic anaemia
Anaemia vitamin B6 deficiency	Macrocytosis
Anaemic hypoxia	Melanaemia
Anaemic retinopathy	Microangiopathic haemolytic anaemia
Aplasia pure red cell	Microcytic anaemia
Aplastic anaemia	Nephrogenic anaemia
Autoimmune anaemia	Normochromic anaemia
Autoimmune aplastic anaemia	Normochromic normocytic anaemia
Autoimmune haemolytic anaemia	Normocytic anaemia
Blood loss anaemia	Pernicious anaemia
Cardiac haemolytic anaemia	Proerythroblast count abnormal
Cold type haemolytic anaemia	Proerythroblast count decreased
Coombs negative haemolytic anaemia	Protein deficiency anaemia
Coombs positive haemolytic anaemia	Radiation anaemia
Copper deficiency anaemia	Red blood cell abnormality
Deficiency anaemia	Red blood cell count abnormal
Dilutional anaemia	Red blood cell count decreased
Erythroblast count abnormal	Reticulocyte count abnormal
Erythroblast count decreased	Reticulocyte count decreased
Erythroid dysplasia	Reticulocyte percentage decreased
Erythroid maturation arrest	Reticulocytopenia
Erythropenia	Scorbutic anaemia
Erythropoiesis abnormal	Sideroblastic anaemia
Erythropoietin deficiency anaemia	Spherocytic anaemia
Haematocrit abnormal	Spur cell anaemia
Haematocrit decreased	Warm autoimmune haemolytic anaemia

Drowsiness

Drowsiness will be analyzed by a customized query defined in [Table 7.8.1: 3](#).

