Table 7.8.1: 3 MedDRA preferred terms for user-defined AE category of Drowsiness

User-defined AE category	MedDRA preferred terms	Scope
Drowsiness	Depressed level of consciousness	Narrow

	Post-injection delirium sedation syndrome	Narrow
	Radiation somnolence syndrome	Narrow
	Sedation	Narrow
	Altered state of consciousness	Broad
	Brain fog	Broad
	Concussion	Broad
	Consciousness fluctuating	Broad
	Intracranial hypotension	Broad
	Lethargy	Broad
	Obstructive sleep apnoea syndrome	Broad
	Orexin deficiency	Broad
	Pickwickian syndrome	Broad
	Post concussion syndrome	Broad
	Presyncope	Broad
	Sedation complication	Broad
	Sleep-related hypoventilation	Broad
	Shift work disorder	Broad
	Sleep apnoea syndrome	Broad

Sleep disorder

Sleep disorder related AE search terms are based upon the FDA Medical Queries (FMQs) of Insomnia (broad) and Somnolence (broad). Refer to [Table 7.8.1: 4](#) for a list of MedDRA preferred terms in each of the groupings.

Table 7.8.1: 4 MedDRA preferred terms for user-defined AE categories of sleep disorder AEs

User-defined AE category	MedDRA preferred terms	
FMQ Insomnia (broad)	Advanced sleep phase	Primary insomnia
	Behavioural induced insufficient sleep syndrome	Psychophysiologic insomnia
	Circadian rhythm sleep disorder	Shift work disorder
	Delayed sleep phase	Sleep disorder due to general medical condition, insomnia type
	Dyssomnia	Sleep disorder due to general medical condition, mixed type
	Early morning awakening	Terminal insomnia
	Fatal familial insomnia	Dysfunctions associated with sleep stages or arousal from sleep
	Hyposomnia	Dyssomnia NOS
	Initial insomnia	Jet lag
	Insomnia	Microsleep
	Insomnia exacerbated	Sleep deficit
	Insomnia NEC	Sleep disorder
	Insomnia related to another mental condition	Sleep disorder due to a general medical condition
	Irregular sleep phase	Sleep disorder NOS
	Irregular sleep wake rhythm disorder	Sleep disorder therapy

	Middle insomnia	Sleep inertia
	Non-24-hour sleep-wake disorder	Sleep study abnormal
	Poor quality sleep	
FMQ Somnolence (broad)	Central nervous system depression NOS	Sedation aggravated
	Consciousness fluctuating	Somnolence
	Depressed level of consciousness	Somnolence neonatal
	Hypersomnia	Stupor
	Infant sedation	Altered state of consciousness
	Lethargy	Fatigue
	Neonatal oversedation	Fatigue aggravated
	Primary hypersomnia	Prostration
	Sedation	Sluggishness

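### The SAP's Drowsiness category (Table 7.8.1: 3) omits the preferred term Somnolence, the term the protocol equates with drowsiness

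*SAP*

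**What the plan says.** SAP 7.8.1 sets up several user-defined AE categories. For one of them it states: "Drowsiness will be analyzed by a customized query defined in" Table 7.8.1: 3, which is headed "MedDRA preferred terms for user-defined AE category of Drowsiness". No other definition of Drowsiness is given. The category is to be tabulated, since the planned outputs include "AEs in user-defined AE categories".

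The protocol says what drowsiness means for this drug. The risk overview in Protocol 1.4.2 lists, among the most frequent CNS-related events, "Somnolence (drowsiness" (the bracket closes in the source). Protocol 1.2.5 adds: "Dizziness, somnolence and gastrointestinal disorders, such as nausea and vomiting, were also among the AEs reported more frequently on Iclepertin than placebo".

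Two other groupings in SAP 7.8.1 cover similar ground: "CNS depressant effects" in Table 7.8.1: 1 and FMQ Somnolence (broad) in Table 7.8.1: 4. Both list Somnolence.

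**The concern.** A category called Drowsiness should count the event that the sponsor itself describes as drowsiness. Table 7.8.1: 3 admits terms such as Concussion, Intracranial hypotension and Pickwickian syndrome but not Somnolence. A patient whose only relevant event is coded to Somnolence is therefore outside the category under both the narrow and the broad scope.

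What is at stake is the accuracy of one safety display. The Drowsiness row could show a low rate beside a higher somnolence rate elsewhere in the same report, with nothing in the SAP to explain the difference. The event is an expected effect of the drug, so the understatement falls on a term that readers will look for.

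**Working it through.** There is no planned figure to reproduce. The check is a count of terms and a comparison of lists.

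**Step 1: contents of Table 7.8.1: 3.**
- Narrow (4): Depressed level of consciousness; Post-injection delirium sedation syndrome; Radiation somnolence syndrome; Sedation.
- Broad (15): Altered state of consciousness; Brain fog; Concussion; Consciousness fluctuating; Intracranial hypotension; Lethargy; Obstructive sleep apnoea syndrome; Orexin deficiency; Pickwickian syndrome; Post concussion syndrome; Presyncope; Sedation complication; Sleep-related hypoventilation; Shift work disorder; Sleep apnoea syndrome.
- Total: 4 + 15 = 19. Entries equal to Somnolence: 0 of 19. One entry contains the word (Radiation somnolence syndrome), but it is a different preferred term.

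**Step 2: comparison with the two related groupings.**

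| Grouping | Terms | Lists Somnolence | Terms shared with Drowsiness |
|---|---|---|---|
| CNS depressant effects (Table 7.8.1: 1) | 9 | Yes | 3: Depressed level of consciousness, Lethargy, Sedation |
| FMQ Somnolence (broad) (Table 7.8.1: 4) | 18 | Yes | 5: those 3, plus Altered state of consciousness and Consciousness fluctuating |

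With overlaps of 3 of 9 and 5 of 18, Drowsiness is not simply a wider version of either list. Hypersomnia is also in both other groupings and absent from Drowsiness.

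**Step 3: could the row have been lost in PDF reading?** The narrow terms run alphabetically, so Somnolence would follow Sedation. There the text passes straight to the first broad term, with no gap and no redaction mark. The one visible break in the table comes after Depressed level of consciousness, where Hypersomnia could fall but Somnolence could not. A lost row is thus possible but is not the natural reading. The SAP history (section 11) records that version 2 repaired a truncation in Table 7.8.1: 2 and mentions no repair to Table 7.8.1: 3. That does not prove the same fault here, but it is a reason to check.

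**Step 4: scale.** The shortfall in an arm equals the share of its patients coded to Somnolence and to no term in Table 7.8.1: 3. The documents give no incidence by preferred term, so this share is unknown. With the 293 patients per arm of Protocol 7.5 and two assumed shares:
- 1%: 293 × 0.01 = 2.93, about 3 patients.
- 2%, the cut-off for the SAP's table of frequent preferred terms: 293 × 0.02 = 5.86, about 6 patients.

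These are conversions to patient numbers, not estimates. The safety analysis uses the Treated Set, so the actual denominator may differ slightly from 293.

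**The case against.** The strongest reply is that nothing is hidden. Somnolence has its own named grouping in Table 7.8.1: 4, sits in the CNS depressant grouping, appears in the system organ class and preferred term table, and enters the frequent-term table if its incidence exceeds 2%. All AE analysis is descriptive, and Protocol 7.2.5 does not call for a Drowsiness category, so no protocol commitment is broken. This stands, and it limits the finding to one display. It does not correct that display, because the other tables are the ones that will show a different picture.

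A second reply is that the groupings serve different purposes (abuse potential, sleep disorder, a customized query), so their counts need not agree. That is true in general. It does not explain why a query named Drowsiness leaves out the term that the protocol glosses as drowsiness, and the SAP offers no reason.

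A third reply is that a row dropped in text extraction would leave the remaining rows adjacent and still in order, and that the broad block is not strictly alphabetical anyway. This also stands in part: the layout cannot prove the list complete. It is why the remedy starts with a look at the source query. Finally, the protocol's gloss sits in a risk table and is not an analysis definition. That is fair, but it is the sponsor's own description of the effect.

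**Conclusion.** The concern holds. Followed as written, Table 7.8.1: 3 gives a Drowsiness count that excludes its core term, and the SAP gives no reason for the exclusion. This is a minor to moderate reporting error in a descriptive safety table, not a lost safety signal. Its size cannot be computed from the documents; it is whatever share of patients is coded to Somnolence alone among the drowsiness-type terms.

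The conclusion assumes that the table as read matches the table in the SAP. Confidence is medium for that reason.

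**What to change.** Compare the whole of Table 7.8.1: 3 with the source query, including whether Hypersomnia belongs. If Somnolence is missing there too, add it with narrow scope before unblinding, so that a safety category is not changed after the results are known. If the omission was deliberate, say so in SAP 7.8.1, give the reason, and point the reader to the groupings that do count somnolence. If the source table already holds the row, no change is needed.

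The cost is one check and one table row. No new data are required.
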